921 covariate because it is a randomization stratification factor. Eyes that receive an alternative
922 treatment for DME will be handled in the same manner as in the primary analysis. If the analyses

923 of imputed and observed data differ substantially, then exploratory analyses will be performed to
924 evaluated factors that may have contributed to the differences. A separate sensitivity analysis will
925 be conducted where no data truncation on outlying values for change in CST will be performed.

926 **7.7 Sensitivity Analysis**

927 An additional sensitivity analysis will be performed, where OCT measurements taken after an eye
928 receives an alternative treatment for DME will be considered as missing and will be imputed using
929 multiple imputation stratified by treatment group. The imputation model will include an additional
930 variable indicating whether the eye receives an alternative treatment, in addition to all variables
931 specified in the primary imputation model.

932 **7.8 Analysis of the Secondary Endpoint(s)**

933 The ITT analysis cohort will be used for all secondary outcomes unless otherwise specified. Eyes
934 that receive treatment for DME (see section 3.6) will have the last measurement prior to treatment
935 used for the secondary analysis unless otherwise specified. Unless otherwise specified, missing
936 data will be imputed with multiple imputation. The imputation model will be stratified by treatment
937 group and include the baseline value of the outcome, the randomization stratification factor, and
938 change in the outcome for the available time points.

939 Change in retinal volume from baseline is a continuous variable and will be analyzed using
940 analysis of covariance. The analysis will include adjustment for baseline CST, baseline retinal
941 volume, and the randomization stratification factor. The estimated treatment-group difference,
942 95% confidence interval and 2-sided P value will be presented. The assumptions of linearity,
943 normality, and homoscedasticity will be verified using graphical methods. Serious violations may
944 be addressed by transformation of dependent and/or independent variables, non-parametric
945 methods, categorizing continuous covariates, and/or excluding covariates.

946 The percentage of eyes with CST below OCT machine and gender-specific threshold for DME at
947 the primary outcome visit is a binary variable that will be analyzed with logistic regression with

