19 Study eyes will be assigned randomly to the two treatment groups in a 1:1 ratio stratified by site
20 and recent (within 4 months) or planned intravitreous treatment in the non-study eye, including
21 intravitreous anti-VEGF and steroid. Participants may have only one study eye enrolled in the
22 randomized trial.

23 **2.0 Efficacy Analysis Plan**

24 **2.1 Primary Outcome Analysis**

25 The primary analysis will consist of a treatment group comparison of mean change in CST from
26 baseline to the primary outcome visit using analysis of covariance, with adjustment for baseline
27 CST and the randomization stratification factor of recent or planned intravitreous treatment in
28 the non-study eye. Given that OCTs can be obtained from either Spectralis or Cirrus images, and
29 that values from these machines cannot be used interchangeably, OCT values will be converted
30 to a common value for reporting and analyses.

31 The primary analysis is an intention-to-treat analysis. All randomized eyes will be included in
32 the primary analysis irrespective of treatment received and will be analyzed according to
33 treatment group assignment at randomization.

34 For the primary analysis, study participants who complete the primary outcome visit without
35 missing data at the primary outcome visit will be considered as the **completer cohort**. Markov
36 chain Monte Carlo (MCMC) multiple imputation with 100 imputations will be used to handle
37 missing data for participants who do not complete the primary outcome visit, i.e., **non-**
38 **completer cohort**. The imputation model will be stratified by treatment group and will include

39 the CST measured at baseline and at all monthly interim visits up to the primary outcome visit
40 along with the randomization stratification factor of recent or planned intravitreous treatment in
41 the non-study eye.

42 For eyes that receive alternative treatment for DME (detailed in Protocol Section 3.6) in Phase 1,
43 data measured after the initiation of the alternative treatment will be considered to be missing
44 before entering the multiple imputation (MI) process, regardless of whether the treatment
45 initiation is per-protocol, and whether the participant completes the primary outcome visit. Then
46 after multiple imputation, the last OCT measurement prior to the initial alternative treatment
47 (LOCF data) will overwrite the MCMC imputed values for all post-treatment visits and will be

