48 used for the primary analysis. It is recognized that LOCF does not reflect the uncertainty in
49 outcomes (i.e., underestimates the variances) and is likely to introduce bias (of unknown
50 magnitude) into the primary analysis that favors the PBM group under the alternative hypothesis,
51 as participants may receive alternative treatment for falsely low visual acuity values, and some
52 eyes meeting criteria for and receiving alternative treatment might have recovered if they'd been
53 left untreated. However, the bias is not being increased by the MI since LOCF is applied after
54 MI. Also, in a recent study for a similar cohort, only 2 (<1%) out of 236 eyes in the observation
55 group initiated treatment without meeting pre-specified criteria during 2 years of follow-up,
56 therefore we expect very few eyes (if any) in this study will receive alternative DME treatment
57 against protocol.

58 To limit the influence of extreme data points, change in CST will be truncated at ± 3 SD after
59 imputation and LOCF to improve robustness of the treatment comparison. The cutoff values for
60 data truncation will be calculated using the primary outcome visit data within the completer
61 cohort, combining treatment groups, i.e. the “**completers’ data**”, which will consist of the
62 observed data for completers without alternative DME treatment, and the LOCF data for
63 completers who receive an alternative DME treatment.

64 Therefore, the **primary analysis dataset** will include:

65 • Data from completers without alternative DME treatment,
66 • MCMC imputed data for non-completers without alternative DME treatment,
67 • LOCF data for participants who receive an alternative DME treatment.

68 The *P* value, adjusted treatment group difference, and associated 95% confidence interval will be
69 reported for the treatment group effect with robust variance estimation using the primary analysis
70 dataset. If the *P* value for the test of the treatment effect is less than or equal to .05, then it will
71 be concluded that there is a significant difference for change in CST at the primary outcome
72 visits between the groups. In other words, if $P \leq .05$, the null hypothesis of no treatment effect
73 will be rejected.

74 Multiple imputation assumes that data are missing at random (MAR). In the present study, this
75 would mean that whether follow-up CST measurements are missing or observed may be a

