102 from statistical models (e.g., treatment group differences, confidence intervals, and P values)
103 will be based on primary analysis data as noted above.

104 **2.1.1 Sensitivity Analyses**

105 Sensitivity analyses for the primary outcome are listed in Table 1. In general, if the sensitivity
106 analysis results differ substantially from the primary analysis results, exploratory analyses will
107 be performed to evaluate factors that may have contributed to the differences.

108

109 **Table 1. Pre-Planned Sensitivity Analyses for the Primary Outcome of Mean Change in**
 110 **CST From Baseline at 4 Months**

| Eyes that receive an alternative DME treatment | Eyes that have missing data at primary outcome visit | Additional details | Rationale |
|--|---|---|---|
| Primary Analysis (MI, LOCF, then data truncation) | | | |
| 
 OCT data after alternative DME treatment will be considered missing for purposes of MI, hence will be imputed in the MI procedure Last OCT measurement prior to alternative DME treatment will then overwrite MI values and will be used for analysis (LOCF). | 
 MCMC multiple imputation for eyes with missing primary outcome data (MI) LOCF values will replace the imputed values for eyes that receive alternative DME treatment | Data truncation: changes in OCT from baseline will be truncated at ± 3 SD after multiple imputation based on cutoff values calculated from completers' data | There is no ideal way to handle eyes receiving alternative DME treatment in analysis. For the primary analysis, LOCF will be used for these eyes. It is recognized that LOCF will tend to bias results towards a larger treatment effect, assuming a treatment effect exists. Sensitivity analyses will be performed to evaluate possible impact of LOCF on study conclusions (#2, #4, #5 below). |
| Sensitivity Analysis #1 (Complete-case analysis with LOCF) | | | |
| LOCF for eyes receiving alternative DME treatment | Complete-case analysis, i.e., only eyes completing primary outcome visit will be included | Same rule for data truncation with primary analysis | To compare primary results including imputed data to results using observed data only. |
| Sensitivity Analysis #2 (MI for ALL eyes missing 4-month visit) | | | |

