| OCT measurement after the alternative DME treatment will be considered missing and will be imputed using multiple imputation | MCMC multiple imputation for all eyes missing the primary outcome visit; imputation model will include an additional covariate indicating whether an eye receives an alternative DME treatment | Same rule for data truncation with primary analysis | To compare if LOCF versus MI for handling eyes receiving alternative DME treatment will produce substantially different results when comparing treatment groups |
| Sensitivity Analysis #3 (No truncation) | | | |
| LOCF (same with primary analysis) | MI, then LOCF for eyes receive alternative DME treatment (same with primary analysis) | No data truncation | To explore if extreme outliers significantly impact the primary analysis results |
| Sensitivity Analysis #4 (Complete-case analysis with transformation in place of truncation) | | | |

| Eyes that receive an alternative DME treatment | Eyes that have missing data at primary outcome visit | Additional details | Rationale |
|--|---|--|--|
| LOCF for eyes receiving alternative DME treatment | Complete-case analysis, i.e., only eyes completing primary outcome visit will be included | Values will be converted to Van der Waerden (Normal) scores for analysis | To examine whether the primary analysis results are robust to: (1) normality assumption; (2) imputation / LOCF of data for those missing the primary outcome visit. |
| Sensitivity Analysis #5 (Complete case analysis without LOCF) | | | |
| Will be excluded from the analysis | Complete-case analysis, i.e., only eyes completing primary outcome visit without alternative DME treatment will be included | 
 • Same rule for data truncation with primary analysis • The analysis will only be performed if 6 (10%) or more eyes receive alternative DME treatment in either group | By excluding eyes meeting criteria for alternative treatment, this analysis is biased towards reduction of treatment effect (assuming a treatment effect exists). Hence, a significant treatment effect in both primary analysis and this analysis would support presence of a true treatment effect. However, a non-significant treatment effect in this analysis cannot be interpreted as evidence for or against a true treatment effect. |

111 2.1.2 Per-Protocol Analysis

112 A per-protocol analysis will be conducted to estimate the treatment effect for each treatment

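### Sensitivity Analysis #2 imputes alternatively treated eyes using an indicator whose effect on the outcome the data cannot estimate

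*SAP*

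**What the plan says.** SAP 2.1 imputes missing CST by MCMC, separately by arm, with 100 imputations. For eyes given alternative DME treatment in Phase 1, "data measured after the initiation of the alternative treatment will be considered to be missing" before imputation, even if the participant attends the primary visit. The last pre-treatment OCT then replaces the imputed value: "LOCF data) will overwrite the MCMC imputed values for all post-treatment visits and will be" used for the primary analysis. The SAP accepts that this probably biases the result in PBM's favour if PBM works.

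Sensitivity Analysis #2 (SAP Table 1) omits that overwrite and keeps the imputed values for treated eyes. Its only other change is that the "imputation model will include an additional covariate indicating whether an eye receives an alternative DME treatment". Protocol 7.7 says the same: a "variable indicating whether the eye receives an alternative treatment, in addition to all variables" of the primary imputation model, again stratified by arm. Neither document states a prior, starting values, the timing that defines the indicator, or a fallback.

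The rationale for the primary analysis in Table 1 names the checks on LOCF: "Sensitivity analyses will be performed to evaluate possible impact of LOCF on study conclusions (#2, #4, #5 below".

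**The concern.** An imputation model can estimate the effect of a covariate on an outcome only from records where both vary and are observed. Here the rule that switches the indicator on also deletes the outcome. The model is asked how treated eyes differ from untreated eyes at the primary visit, having removed every value that could answer.

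At stake is the SAP's main check on an acknowledged bias. If #2 can agree or disagree with the primary result according to seed or prior, agreement gives no reassurance. Disagreement would trigger the exploratory work that SAP 2.1.1 prescribes when results differ substantially, for no real reason.

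**Working it through.** **Planning figures.** The protocol (7.3.2) uses SD 50, difference 30, 90% power and two-sided 5%. The normal formula gives 2 × (1.960 + 1.282)² × 50² / 30² = 58.4, so 59 per arm. The t-test version gives 60 per arm, 120 in total (power 0.903), as stated. 120 / 0.9 = 133.3, so 134, or 67 per arm. The plan gives no figure for #2 itself.

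**Identification.** Within one arm, let A be the indicator, S the stratification factor, and write

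primary-visit CST = b0 + b1·baseline CST + b2·S + b3·interim CSTs + g·A + error.

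- Eye treated before the primary OCT: A = 1, outcome missing by rule.
- Eye with an observed primary outcome: A = 0.
- Untreated dropout: A = 0, outcome missing.

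Among eyes with an observed outcome A sums to 0, and the columns intercept, baseline CST, S and A have rank 3 of 4. Nothing in the data bears on g, yet each treated eye's imputed value contains it. Because imputation is by arm, the other arm cannot help. Pre-treatment interim visits inform the link between A and interim CST, but not g.

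**Effect on the pooled result (illustrative).** Assumptions: MCMC read as multivariate-normal data augmentation; 67 eyes per arm; SD 50; true difference -30; 6 dropouts per arm; 100 imputations (20 for the last two rows); truncation at 3 SD (-171 to +135 for the 5 + 2 dataset); robust ANCOVA with Rubin pooling; one dataset per treated-eye scenario. Six seeds per model, four for the last two rows.

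| Treated eyes (sham + PBM) | Model | Difference, microns | SE |
|---|---|---|---|
| 5 + 2 | LOCF primary | -33.2 | 8.7 |
| 5 + 2 | #2 without indicator | -31.2 to -31.8 | 8.7–8.8 |
| 5 + 2 | #2 as written, non-informative prior | -20.4 to -40.6 | 10.8–14.9 |
| 3 + 1 | #2 without indicator | -36.3 to -37.1 | |
| 3 + 1 | #2 as written | -28.8 to -45.2 | |
| 5 + 2 | with indicator, ridge prior | -29.2 to -31.3 | 10.7–11.2 |
| 5 + 2 | with indicator, one eye per arm coded 1 with an observed outcome | -30.2 to -31.3 | |

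For 5 + 2 as written, one seed gives -20.8 / 14.9 = -1.40 (P = 0.16) and another -40.6 / 11.4 = -3.56 (P = 0.0004), on the same data. Mean imputed change in the treated sham eyes was 35 to 39 microns without the indicator and -773 to +1343 with it. A separately coded run with 3 + 1 treated eyes and other assumed correlations (four seeds) gave -27.8 to -28.4 without and -17.2 to -34.2 with.

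**Starting values and prior.** One simulated arm: 67 eyes, 6 treated, 6 other dropouts, true mean change in treated eyes +17.

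- Indicator in, Jeffreys prior: mean imputed change -581 and -430 (two seeds, start -200), -378 and -307 (start 0), -16 and -129 (start +200).
- Indicator in, ridge prior: no dependence on start in the setting run from both starts, but the prior shapes the answer. Mean +8 to +13, SD 41–50 for a weak ridge; mean 0 to +9, SD 24–30 for a stronger one.
- Indicator out: +17 to +18, SD 14–15, from either start.

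**Bound from truncation.** At SD 50 the cut is 3 × 50 = 150 microns, so k treated eyes can move an arm mean by at most k × 150 / 67 from the centre: 2.2 microns for 1 eye, 6.7 for 3, 13.4 for 6.

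**Other checks on LOCF.**

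- #4 keeps LOCF for treated eyes that complete the visit. Its own rationale covers only "imputation / LOCF of data for those missing the primary outcome visit".
- #5 drops treated eyes, but "The analysis will only be performed if 6 (10%) or more eyes receive alternative DME treatment in either group", and the SAP calls a non-significant result uninformative.
- The tipping-point analysis shifts only eyes without alternative treatment.
- The per-protocol analysis (SAP 2.1.2) drops treated eyes but needs more than 10% excluded and keeps only eyes with at least 70% of sessions. The planned allowance, (134 - 120) / 134 = 10.4%, would just meet that trigger; 13 losses (9.7%) would not by themselves.

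#2 is thus the only listed LOCF check that always runs and removes LOCF for every treated eye.

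**The case against.** The rank result is hard to dispute; the case against concerns size and consequence.

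- **Few eyes may be treated.** The protocol excludes eyes expected to need treatment, and section 3.6 restricts when it may be given. In a further simulated dataset, one treated sham eye gave -34.7 to -37.8 with the indicator against -36.3 to -36.7 without; two gave -32.0 to -39.3 against -36.6 to -36.9, with P below 0.01 throughout. This stands: the damage grows with the count and truncation caps it. The SAP's 2 of 236 does not settle the count, because it covers only treatment started without meeting criteria.
- **The failure would be obvious.** Imputed means of many hundreds of microns would alert anyone who looked. This is partly right, but neither document asks for that inspection, truncation removes the extremes before analysis, and a ridge prior gives plausible values that are still set by the prior.
- **The indicator may not always be 0.** An eye first treated at the primary visit after imaging could be coded 1 with its outcome observed, and results are then stable. This stands as a gap in the definition, but the effect would rest on one or two eyes.
- **Defining timing and prior would be enough.** That makes #2 reproducible. It does not make the effect estimable.
- **#4 does test LOCF in part,** since it drops treated eyes that miss the visit. True, but not for treated completers.
- **The primary conclusion is untouched,** and this is a pilot. True, and it limits how serious the point is.

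**Conclusion.** The concern holds. As written, the indicator in #2 has no identified effect on the primary-visit CST. This follows from the plan's own set-to-missing rule and imputation by arm, and needs no simulation. Under a non-informative prior the treated eyes' imputed values depend on seed and starting values; under a proper prior they depend on that prior. Under sequential regression the indicator would be a constant column and drop out, but the plan specifies MCMC.

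The size is conditional. With assumed counts of 3 + 1 or 5 + 2 treated eyes, the pooled difference moved by roughly 16 to 20 microns across seeds (45.2 - 28.8 = 16.4; 40.6 - 20.4 = 20.2), against a design difference of 30. With one or two treated eyes it moved by a few microns. The documents give no alternative-treatment rate for this trial, and the correlations were assumed, so these figures are illustrative. The primary decision rule is not affected; the interpretability of its main LOCF check is. This should be corrected before analysis.

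**What to change.** In SAP Table 1 (#2) and Protocol 7.7, delete the alternative-treatment indicator. Impute treated eyes from baseline CST, pre-treatment interim CST and the stratification factor, as the primary procedure already does before the LOCF overwrite. Preferably add pre-treatment visual acuity, which is already collected and is what triggers alternative treatment.

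If the indicator is kept, define its timing, including an eye treated after imaging at the primary visit, and state the prior.

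In the primary-analysis rationale of Table 1, do not list #4 as a check on LOCF in treated completers. #5 can stay as it is.

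Optionally, add one delta-shift run on the treated eyes' imputed values, over a range the sponsor justifies.

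Cost: one covariate deleted in two places, one rationale cell reworded, and, if adopted, one added covariate and one extra run. The downside is that #2 then assumes treated eyes would have followed untreated eyes with the same pre-treatment history. That should be stated, and the delta-shift run would probe it.
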